Recently, dentalAEGIS stated Ivoclar Vivadent's Adhese® Universal with VivaPen® as an effective delivery for all etching/adhesive methods; Tysowsky describes the characteristics of the material itself as technique-tolerant and predictable. It forms a stable and homogenous layer that is not sensitive to any application method. "Its hydrophilic solvent, which is acetone-free, provides for optimum wetting of the dentin and enamel, which leads to enhanced infiltration and optimum sealing of the dentinal tubules, preventing microleakage and associated postoperative sensitivity" (28). Although the role of in vitro data to predict clinical performance is increasingly recognised, randomised controlled trials (RCTs) remain the most rigorous study design for assessing the clinical effectiveness of an intervention, a health product or a medical device, especially when they are already commercially available. The majority of

studies investigating the clinical effectiveness of bonding systems use the longevity of restorations in NCCLs as the outcome (3). These are widely available and are normally used in clinical research, for assessment of adhesive systems (26,29) performance and efficacy, because NCCLs present no macro-mechanical retention, they present margins in enamel and/or dentin, and restorations are exposed to high stress during masticatory function (3,17), are located mainly in dentine, facilitating evaluation of the resin–dentine bond which is less stable than the resin–enamel bond (3).

The overarching goal of this RCT is to compare clinical performance at 24th month recall, of two MM adhesives from different manufactures, applied by SE or ER modes, with an SE-all-in-one adhesive (by SE or SE-EE modes) in NCCLs, using both USPHS and FDI criteria.

Objectives and Hypothesis

The purpose is to evaluate/compare clinical effectiveness of dual cure (DC) all-in–one Self-Etch (Futurabond®DC-FBDC) adhesive and the multimode (MM) (FuturabondU® -FBU- and Adhese®Universal –ADU-) adhesives, with or without selective enamel etching, in NCCL restorations, at 24th months follow-up, using Word Dental Federation (FDI) and United States Public Health Services (USPHS) criteria.

The null hypotheses are:

H0 – Bonding to NCCLs with FBDC by Self-Etch mode (FBDC-SE; G1) and MM adhesives by SE mode (MM-SE; G4G6) result in similar (no significant differences) clinical (aesthetic, functional and biologic) behaviour/performance;

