H0 – Bonding to NCCLs with FBDC-SE (G1) and MM-SE(G4G6) result in similar restorations (aesthetic, functional and biologic) success rates;

H0 – Bonding to NCCLs with FBDC-SE (G1) and MM-SE (G4G6) adhesives result in similar restoration retention rates;

H0 – Bonding to NCCLs with FBDC by SE and enamel etching mode (FBDC-SE-EE; G2) and MM adhesives by Etch-and-Rinse mode (MM-ER; G3G5) result in similar (no significant differences) clinical (aesthetic, functional and biologic) behaviour/performance;

H0 – Bonding to NCCLs with FBDC-SE-EE (G2) and MM-ER (G3G5) result in similar restorations (aesthetic, functional and biologic) success rates;

H0 – Bonding to NCCLs with FBDC-SE-EE (G2) and MM-ER (G3G5) result in similar restoration retention rates;

H0 – Bonding to NCCLs with FBDC (G1G2) or FBU (G3G4), DC adhesives, and ADU (G5G6) light-curing adhesive, with SE or SE-ER/ER modes result in similar (no significant differences) clinical (aesthetic, functional and biologic) behaviour/performance;

H0 – Bonding to NCCLs with FBDC (G1G2) or FBU (G3G4) and ADU (G5G6) lightcuring adhesive, with SE or SE-ER/ER modes result in similar restorations (aesthetic, functional and biologic) success rates;

H0 – Bonding to NCCLs with FBDC (G1G2) or FBU (G3G4) and ADU (G5G6) lightcuring adhesive, with SE or SE-ER/ER modes result in similar restoration retention rates;

H0 - FDI or USPHS criteria evaluation outcomes not differ for the same data, at 24th month follow-up.

2 – POPULATION, MATERIALS AND METHODS

2.1- TRIAL DESIGN

The trial design follows the Consolidated Standards of Reporting Trials (CONSORT) statement (30). Prospective, double blind, clinical trial; randomized allocation of NCCL restorations by six adhesion interventional groups (6 arms) for examination of restorations performance.

Study will take place in University

Dentistry School Clinic. Participants recruitment between November 2015 and April 2016. Restorations estimated to be done until April or May 2016 year.

-

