Study variable definition_- Clinical/direct observation and performance evaluation acceptance by means of FDI (*FDI World Dental Federation - clinical criteria for the evaluation of direct restorations*) (Adapted from (33) (Annex 3) and USPHS (34) (Annex 4).

2.7- DATA AND STATISTICAL ANALISYS PLAN (SAP)

Data statistical analysis and description according to aims of this trial; Specific program for statistical data analysis (IBM(c) SPSS(c) Statistics vs. 22 or later) will be used. The changes in parameters clinical performance (paired comparison analysis) by both, FDI and USPHS criteria will be assessed by McNemar or Wilcoxon tests, for both

primary and secondary outcomes, to determine differences between treatments with regard to aesthetic, functional and biological parameters from baseline to 24th month recall (longitudinal assessment). Differences will be considered to be significant at P<0.05. Whenever 3 groups will be compared at 24 months' recall, a Kruskal Wallis test will be used and upon significant differences detection, then Mann-Whitney tests considering Bonferroni correction will be used for pairwise group comparisons.

Comparison of FDI and USPHS acceptance (success rate) criteria evaluation outcomes for Esthetic, for Functional and for Biological Parameters, at 24th Month Follow-up, were compared using the chi-square test.

If missing data occurs, that is, if dropouts or non-observed due to loss of retention of the restoration, then the paired comparison will consider for the baseline just the restorations existing at the last moment (24 months).

2.8- OBSERVATIONS REGARDING SAMPLE CALCULATION

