It was assumed that the minimum number of adhesive restorations to be held in each of the six arms (G1 to G6) is 35 (210 restorations). The researchers did not have detailed information that allows the estimation of the sample size based on power analysis (the effect of the expected difference to the end of the time considered for the study). Thus, in principle they assumed the rules of thumb, usually considered in research situations where there is no advance information concerning the performance evaluation of these adhesive medical devices available on the market, using this assay. Moreover, when considering a "simple" analysis comparison using a McNemar test (repeated measures) in six groups would be necessary in total, including at least 80 cases (to restore teeth) in the sample. When considering at least 35 restorations by group, researchers are greatly increasing the minimum number stipulated in the aforementioned technique. In addition, clinical studies previously performed on this issue (between 2004 and 2012) relative to the post-market clinical evaluation performance of adhesive products/use mode in NCCLs, in the context of restorative dentistry field, has enabled to measure a minimum of 30 restorations as viable for determining events in a short/mean-term as the clinical performance evaluation of a similar nature of adhesives.

2.9- GOOD CLINICAL PRACTICE FOR CLINICAL RESEARCH

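### Section 2.7 asks paired baseline-to-24-month tests to show differences between treatments; they test change over time, and the planned between-arm test is not tied to the hypotheses

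*Combined protocol and SAP*

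**What the plan says.** Section 2.7 of the combined protocol and SAP says that changes in the FDI and USPHS parameters, for primary and secondary outcomes, "will be assessed by McNemar or Wilcoxon tests". It gives the purpose as "to determine differences between treatments with regard to aesthetic, functional and biological parameters from baseline to 24th month recall (longitudinal assessment". The significance level is 0.05; sidedness is not stated.

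The same paragraph continues: "Whenever 3 groups will be compared at 24 months' recall, a Kruskal Wallis test will be used", with Bonferroni-corrected Mann-Whitney tests after a significant result. No arms, outcomes or hypotheses are named. The chi-square test in this section compares FDI with USPHS, not arms.

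Missing data are said to include dropouts and restorations "non-observed due to loss of retention of the restoration". The rule that section 2.7 sets for both cases reads: "then the paired comparison will consider for the baseline just the restorations existing at the last moment (24 months". Section 2.8 discusses sample size by reference to "using a McNemar test (repeated measures) in six groups".

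Objectives and Hypothesis lists ten nulls. Nine form three families (G1 with G4 and G6; G2 with G3 and G5; the three products), each covering performance, success and retention. Typical wording is "MM adhesives by SE mode (MM-SE; G4G6) result in similar (no significant differences) clinical" and "FBDC-SE-EE (G2) and MM-ER (G3G5) result in similar restoration retention rates". The tenth compares FDI with USPHS.

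**The concern.** The stated purpose of the paired tests does not match what they can show. A baseline-to-24-month test on the same restorations asks whether scores moved. Nine of the ten nulls ask whether adhesives or modes differ from one another.

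The words about outcomes and treatment differences are attached to the paired tests, while the between-arm test carries only a general condition. Someone applying section 2.7 literally could therefore report a p-value for change over time as the answer to a question about adhesives. That could suggest a difference where the arms are alike, or hide a real one where all arms deteriorate.

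Retention is the sharpest case. The paired set contains only restorations still present at 24 months, so complete loss cannot appear in it.

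**Working it through.** **What is paired.** Three places settle this. The sentence describes a longitudinal assessment of changes; the missing-data rule cuts the baseline to restorations still present at 24 months; and section 2.8 calls McNemar a repeated-measures test. Pairing different arms within a participant is nowhere described. It would not always be possible either, because section 2.2 allows a participant to contribute a single lesion.

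**The plan's own figures.** 6 arms × 35 = 210, and 35 sequences × 6 = 210, so these agree. The 80 cases that section 2.8 gives for McNemar (80/6 ≈ 13.3 per group) cannot be reproduced, because no discordant proportions, power or sidedness are given. Nothing below depends on that figure.

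**Inputs for the examples.** 35 restorations per arm (Table 1, section 2.8) and alpha 0.05 (section 2.7). Assumed: two-sided tests, one dichotomised criterion, all restorations acceptable at baseline, worsening only, and independent restorations. The counts are invented.

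**Formulas.**
- Exact McNemar in one arm with b worsened and none improved: p = 2 × 0.5^b. Hence b=5 gives 0.0625, b=6 gives 0.031, and b=18 gives 0.0000076.
- Kruskal-Wallis on the 0/1 outcome at 24 months, three arms of n=35, N=105: H = ((N−1)/N) × Σ(x_i − x̄)² / (n·p̂·(1−p̂)), with p = exp(−H/2) on 2 df.

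**Example 1: arms alike, paired verdicts differ.** Worsened 6/5/5.
- McNemar per arm: 0.031 / 0.063 / 0.063.
- Between arms: p̂ = 16/105 and Σ(x_i − x̄)² = 0.667, so H = (104/105) × 0.667/4.521 = 0.146 and p = 0.93.

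**Example 2: arms differ, paired verdicts agree.** Worsened 6/6/18.
- McNemar per arm: 0.031 / 0.031 / 0.000008, all significant.
- Between arms: p̂ = 30/105 and Σ(x_i − x̄)² = 96, so H = (104/105) × 96/7.143 = 13.31 and p = 0.001.

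**If the paired test were run over three arms together.** Section 2.7 does not say which is meant, although the wording of section 2.8 leans towards per-arm use. With 18 of 105 worsened, McNemar p is 0.0000076 for any split. Kruskal-Wallis gives p = 1.0 for 6/6/6 and p = 0.0000035 for 0/3/15 (H = 25.10).

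**Retention.** Suppose losses are 0/0/8.
- The paired set is 35/35/27. If the rest are unchanged, no pair is discordant and the paired test shows nothing.
- If losses are scored at 24 months: p̂ = 8/105 and Σ(x_i − x̄)² = 42.67, so H = (104/105) × 42.67/2.463 = 17.15 and p = 0.0002.
- The annexes already supply the scores. Annex 3 puts loss at FDI 4.5, and Annex 4 has a Retention level, Charlie, for a missing restoration.

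**The case against.** The strongest reply is that this is one loose clause in a paragraph that already contains the right kind of test. The sentence opens and closes with language about change over time, and the 24-month group comparison is then given to Kruskal-Wallis with corrected pairwise tests. Every one of the nine hypotheses involves three adhesives, so the three-group condition fits G1/G4/G6, G2/G3/G5 and G1G2/G3G4/G5G6. Much of this stands, and it makes the problem modest. What remains is that the stated purpose is wrong and the link is left to the reader.

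Four stronger readings are tempting and should not be drawn:

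- **That the plan has no between-arm test, or leaves the choice wide open.** It has one. Writing G4G6 and G3G5 as single terms, or setting two dual-cure products beside a light-curing one, might suggest two-group contrasts, for which section 2.7 names no between-arm test. But section 2.7 says nothing of pooling, and the three-group reading fits throughout.
- **That lost restorations drop out of the 24-month comparison.** The exclusion is confined to the paired comparison. Section 2.6 requires scoring at each recall, and both annexes score loss. Section 2.7 lists loss of retention under missing data without saying that it will be scored, so a clarification is enough.
- **That the paired results say nothing about the arms.** Run per arm, they reflect each arm's count of worsened restorations. They are descriptive, but not a valid test of a difference.
- **That identical arms would be declared different at some calculable rate.** This needs a rule that significance in one arm but not another means a difference. The SAP states no such rule, and any rate would also rest on assumed worsening and independent arms.

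**Conclusion.** The point holds as a mismatch between the stated purpose and the test, together with an unwritten link between hypotheses and test. A paired baseline-to-24-month test cannot decide the nine between-adhesive nulls; this follows from what is paired and needs no assumed rate. The examples show that it can mislead in both directions: conflicting per-arm results with between-arm p=0.93, and uniformly significant per-arm results with between-arm p=0.001.

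The p-values are illustrations under the stated assumptions. They treat restorations as independent, although one participant may contribute up to six; this applies to the Kruskal-Wallis figures as well. The 35-per-arm examples match the first two hypothesis families. The product comparison, with both modes combined, would have 70 per group.

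The plan is worth correcting, but the suitable kind of comparison is already in it, so the defect is one of specification rather than of design.

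**What to change.** 1. Reword section 2.7 so that McNemar and Wilcoxon results describe change from baseline to 24 months within each arm, and say that they are not used to claim differences between treatments.
2. State that each of the nine between-adhesive hypotheses is decided by the planned 24-month three-group comparison: G1/G4/G6, G2/G3/G5, and G1G2/G3G4/G5G6. The schedule in section 3 places the 24-month evaluation between November 2017 and May 2018, and the documents do not say whether those data had been examined when this text was settled. If they have been seen, label the mapping post hoc.
3. Base the retention hypotheses on the 24-month comparison. Score observed losses as the annexes provide (FDI 4.5; USPHS Retention, Charlie) and treat only dropouts as missing. The relevant USPHS score is the one under Retention, not the Delta level under Marginal Integrity.

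The cost is small: a few sentences and minor analysis work, with no new data. The paired results stay as description, so no planned output is lost.

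### Section 2.7 applies P<0.05 to primary and secondary outcomes alike, names no primary outcome, and corrects only post-hoc pairs, so error across the nine adhesive nulls, two scales and 16 items is uncontrolled

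*Combined protocol and SAP*

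**What the plan says.** Section 2.7 (SAP) states: "Differences will be considered to be significant at P<0.05". The paired baseline-to-24-month tests on both scales are McNemar or Wilcoxon tests and cover "primary and secondary outcomes, to determine differences between treatments with regard to aesthetic, functional and biological parameters". The SAP thus assumes that primary and secondary outcomes exist, but the supplied text does not say which is which.

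For three-group comparisons at 24 months, "a Kruskal Wallis test will be used and upon significant differences detection", "Mann-Whitney tests considering Bonferroni correction will be used for pairwise group comparisons". No other adjustment is stated.

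Objectives and Hypothesis lists ten nulls without ranking them. Nine concern adhesives: three contrasts, each for behaviour/performance, success rate and retention rate. The contrasts are G1 against G4 and G6; G2 against G3 and G5; and product against product. The tenth compares FDI with USPHS. Annexes 3 and 4 define 8 items on each scale, and the Annex 2 form records each item separately.

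**The concern.** The Bonferroni step protects pairwise comparisons inside one three-group test of one variable. It does not reach across items, scales, contrasts or the nine adhesive nulls, each of which can be declared significant at 0.05. With no primary outcome, one significant item on one scale can be reported as a difference between adhesives, and the item can be picked once results are known.

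The Introduction shows that the choice can matter. It describes an 18-month trial of another universal adhesive in which use modes differed only on marginal adaptation, by FDI but not by USPHS.

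**Working it through.** The documents state no family-wise error rate, so there is no planned figure to reproduce.

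**Inputs from the documents.** Per-test level 0.05 (section 2.7); nine adhesive nulls in three contrasts (Objectives and Hypothesis); 8 FDI and 8 USPHS items (Annexes 3 and 4); 35 restorations per arm, 6 × 35 = 210 (section 2.8).

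**Not in the documents, so assumed.** The number of tests per null, the correlation between tests, and the share of restorations scored below the top grade.

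**1. Independent tests, all nulls true.** P(at least one false positive) = 1 − 0.95^k.
- One test per adhesive null, k = 9: 1 − 0.95^9 = 0.370.
- One contrast, all items, k = 16: 1 − 0.95^16 = 0.560.
- Three domains × two scales × three contrasts, k = 18: 1 − 0.95^18 = 0.603.
- All items in three contrasts, k = 16 × 3 = 48: 1 − 0.95^48 = 0.915, with 48 × 0.05 = 2.4 false positives expected.

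**2. Correlated tests.** Take two-sided normal statistics with common correlation r as a stand-in. Then P = 1 − ∫ φ(u) [Φ((1.96 − √r·u)/√(1−r)) − Φ((−1.96 − √r·u)/√(1−r))]^k du. For k = 48 this gives 0.61 at r = 0.5 and 0.40 at r = 0.7. For k = 9 it gives 0.27 and 0.20.

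**3. Effect of sparse scores and of the planned Bonferroni step.** All-null data were simulated with 35 per arm, 16 three-level items and the three contrasts read as three-group Kruskal-Wallis tests. Significant results were followed by pairwise tests at 0.05/3 = 0.0167. Items ranged from independent to strongly correlated, and there were 1,000 trials per setting.

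| Assumed share below top grade | Any Kruskal-Wallis P<0.05 among 48 | Any pair also passing Bonferroni |
|---|---|---|
| 30% on every item | 68–86% | 61–81% |
| Mixed, 2–30% | 69–82% | 54–68% |
| Sparse, 1–10% | 66–77% | 43–53% |
| 3% on every item | 66–75% | 16–17% |
| 1% on every item | 33–42% | 0.3% or less |

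Teeth within a participant were treated as independent.

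**4. With one primary outcome.** Three contrasts at 0.05 each, if independent: 1 − 0.95^3 = 0.143. At 0.05/3 each: 1 − (1 − 0.0167)^3 = 0.049. Holm also keeps the overall level at or below 0.05, whatever the correlation.

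**The case against.** The case against a strong claim has several parts.

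- **The unit of testing is inferred.** Section 2.7 never says that all 16 items will be tested in every contrast. One test per adhesive null gives 37% at most under independence, and less if the tests are positively correlated. This stands, but even the 20% at r = 0.7 is four times the nominal level. The plan also defines no single variable that would supply one test for behaviour or for success.
- **Correlation and sparsity lower the figures.** Several FDI and USPHS items score nearly the same feature of the same tooth, and the product contrast reuses the arms of the other two. This stands, and it is why only a range can be given.
- **Bonferroni is present.** This stands. A pairwise claim must pass two steps, and with very sparse scores few false ones would.
- **The listed nulls limit the contrasts.** This stands. The freedom to choose concerns items and scales, not arbitrary pairs of arms.

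A reader might infer that a false adhesive difference is simply likely. The documents do not support that, because they give none of the rates or correlations on which it depends. A reader might also add the baseline-to-24-month tests and the FDI-versus-USPHS tests to the count. These address change over time and agreement of scales. They are not comparisons of adhesives and should be left out, although the SAP loosely describes the paired tests as determining differences between treatments.

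**Conclusion.** The point holds in a limited form. Followed exactly, section 2.7 leaves the error rate uncontrolled across nine adhesive nulls, two scales and up to 16 items, and it leaves the primary outcome open. This is a property of the stated decision rule and goes beyond missing detail.

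The chance of at least one false omnibus result is 37% for nine independent tests. For 48 tests it is 91% if independent, about 61% at correlation 0.5 and 40% at 0.7. It falls further for very sparse scores and for differences that must survive the pairwise step.

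A reader might also infer that the primary outcome was, or will be, chosen after seeing results. The Project Schedule places the 24-month evaluation between November 2017 and May 2018, and reference access dates run to November 2018, so this version appears to follow data collection. That does not show when any choice was made, or that data had been reviewed. It is a reason to ask for the date. A page was also removed before review, so the finding is only that the supplied text names no primary outcome.

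**What to change.** In section 2.7:

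1. Name one primary outcome and the scale that defines it. Retention at 24 months is a natural candidate, because it already has its own three nulls and the Introduction says that most studies of bonding systems "use the longevity of restorations in NCCLs as the outcome". The documents do not make it primary, however. If another primary outcome was declared before data review, keep that one.
2. If retention is used, state how partial loss counts. FDI item 4 puts partial and complete loss in its worst grade, whereas USPHS separates partially retained from missing.
3. Test the three contrasts of the primary outcome with Holm at an overall 0.05: thresholds 0.0167, 0.025 and 0.05 in order of increasing P.
4. Report the other nulls, items and scales as secondary, with estimates and confidence intervals, and label any P values as unadjusted and exploratory.
5. State the date of the choice relative to data review. If it was made after the 24-month data were seen, label all the analyses exploratory.

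The cost is SAP wording, a stricter threshold for the three primary tests, and no confirmatory claims on the six other adhesive nulls or the FDI-versus-USPHS null. The change does not supply the power basis that section 2.8 says was unavailable.
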